9.2. Identification of Differentially Expressed Genes

Negative binomial generalized linear models as implemented in the edgeR software [10] will be applied to identify differentially expressed (DE) genes after exclusion of outlying samples and lowly expressed genes. TMM-adjusted total read counts per sample will be included in the models as an offset to account for systematic sample differences. If systematic technical bias is detected and the effect is balanced across study arms, it will be accounted for by including a covariate or factor as part of the negative binomial models.

For all study arms, DE gene analysis will be carried out for each post-first vaccination study day (Day 2, 4, 8 or 29) in relation to pre-first vaccination gene expression levels (Section 9.2.1). For Study Arms 2 and 3, DE gene analysis will be carried out for each post-second vaccination study day (Day 30, 32, and 36) in relation to pre-second vaccination (Day 29) gene expression levels (Section 9.2.2). In addition, differences in DE gene responses between Study Arms will be assessed for all possible pairwise study arm comparisons (Section 9.2.3).

To control for testing multiple genes, the false-discovery rate (FDR) based on the Benjamini-Hochberg procedure [12] as implemented in the *p.adjust* R function will be applied for each model. In all cases, genes with an absolute fold change (effect size) of ≥ 1.5 compared to pre-vaccination or between Study Arms and FDR-adjusted p-value < 0.05 will be considered significantly DE. Depending on observed magnitude of differential expression effects, the pre-specified fold change cut off of 1.5-fold may be revised. The number of DE genes will be tabulated by study arm and time point (Table 126 and Table 127). In addition, DE gene listings that include gene annotations, \log_2 fold change estimates, p-values, FDR-adjusted p-values, likelihood ratio statistic and average LCPMs will be provided for each post-vaccination day (Table 128).

Treatment effects in terms of overall fold changes and FDR-adjusted p-values will be summarized for all genes that passed the low expression cut off using MA plots and Volcano plots (Figure 9). Overlap in DE genes between post-vaccination days and Study Arms will be summarized using UpSet plots as outlined in Figure 10 both in terms of overall numbers and separately for up/down-regulated DE genes.

The following sections describe the negative binomial model parameterization and hypotheses that will be tested.

9.2.1. Identification of DE Genes Compared to Pre-First Vaccination

For each post-first vaccination day and study arm, a negative binomial model will be fit to pre- and post-first vaccination read counts. Each model will include coefficients to estimate subject and pre- vs. post-first vaccination effects. The subject effects for estimating subject-specific pre-first vaccination levels will be added to account for paired samples from the same subject. Effects will be parameterized in the design matrix using dummy variables with one variable for each subject and an additional variable for the vaccination effect. For vaccination effects, the value will be set to 1 for post-first vaccination and 0 for pre-first vaccination observations. For each gene, the statistical significance of the post- vs. pre-vaccination effect will be evaluated using a likelihood ratio testing the following hypothesis on the \log_2 scale:

$$H_0: \mu_{\text{post-vaccination}} - \mu_{\text{pre-vaccination}} = 0, H_1: \mu_{\text{post-vaccination}} - \mu_{\text{pre-vaccination}} \neq 0$$

Genes with an absolute fold change (effect size) of ≥ 1.5 compared to pre-first vaccination and FDR-adjusted p-value < 0.05 will be considered to be significantly DE.

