6.8. Multiple Comparisons/Multiplicity

No multiple testing adjustments will be carried out for the safety, immunogenicity, and cytokine/chemokine endpoints. For -omics endpoints, the false-discovery rates (FDR) based on the Benjamini-Hochberg procedure as implemented in the R *p.adjust* function will be used to control the false positive rate among significantly differentially expressed genes, proteins, and enriched pathways.

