9.1.6. Determination of Cut Offs for Filtering Lowly Expressed Genes

Transcriptome-wide LCPM results will be used to identify a suitable minimum LCPM filter cut off to exclude lowly expressed genes excluding outlying samples. Genes with mean normalized expression levels below X log₂ counts per million across all samples (all study arms and time points) will be considered to be lowly expressed and will be excluded from the differential expression analysis. To determine a suitable cut off value for X, reverse cumulative distribution function (RCDF) plots summarizing the percentage of genes that exceeded a certain LCPM cut off will be plotted on the y-axis (Figure 8). The goal is to choose a cut off that retains between 10,000 and 14,000 genes for differential analysis. A default cut off of 1 count per million will be used if the targeted gene coverage is met. The filtered set will be used as input for down-stream transcriptomics endpoint analysis described in subsequent sections.

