9.2.2. Identification of DE Genes Compared to Pre-Second Vaccination

For subjects receiving a second vaccination, for each post-second vaccination day (Day 30, 32, and 36) and study arm (Study Arms 2 and 3), a negative binomial model will be fit to pre- and post-second vaccination read counts across subjects. The model will be parameterized and evaluated as described in Section 9.2.1, except using Day 29 as the pre-vaccination reference.

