14.3 Transcriptomics Data

Table 126: Genes Differentially Expressed Compared to Pre-Vaccination by Treatment Group, Cell Type, and Post-Vaccination Day

		Study Arm 1 A/H3N2v, D1 (N=X)	Study Arm 2 A/H7N9 + AS03, D1, 29 (N=X)	Study Arm 3 A/H7N9 + PBS, D1, 29 (N=X)
Time Point	Cell Type	DE Genes [#]	DE Genes [#]	DE Genes [#]
Day 2 (Post Vaccination 1 vs. Pre-Vaccination 1)	Monocytes	xxx	xxx	xxx
	Dendritic cells	xxx	xxx	xxx
	Neutrophils	xxx	xxx	xxx
	NK-cells	xxx	xxx	xxx
	T-cells	xxx	xxx	xxx
	B-cells	xxx	xxx	xxx
Day 4 (Post Vaccination 1 vs. Pre-Vaccination 1)	Monocytes	xxx	xxx	xxx
	Dendritic cells	xxx	xxx	xxx
	Neutrophils	xxx	xxx	xxx
	NK-cells	xxx	xxx	xxx
	T-cells	xxx	xxx	xxx
	B-cells	xxx	xxx	xxx
Day 8 (Post Vaccination 1 vs. Pre-Vaccination 1)	Monocytes	xxx	n/a	n/a
	Dendritic cells	xxx	n/a	n/a
	Neutrophils	xxx	n/a	n/a
	NK-cells	xxx	n/a	n/a
	T-cells	xxx	n/a	n/a
	B-cells	xxx	n/a	n/a
Day 29 (Post Vaccination 1 vs. Pre-Vaccination 1)	Monocytes	n/a	xxx	xxx
	Dendritic cells	n/a	xxx	xxx
	Neutrophils	n/a	xxx	xxx
	NK-cells	n/a	xxx	xxx

		Study Arm 1 A/H3N2v, D1 (N=X)	Study Arm 2 A/H7N9 + AS03, D1, 29 (N=X)	Study Arm 3 A/H7N9 + PBS, D1, 29 (N=X)
	T-cells	n/a	xxx	xxx
	B-cells	n/a	xxx	xxx
Day 2 (Post Vaccination 2 vs. Pre-Vaccination 2)	Monocytes	n/a	xxx	xxx
	Dendritic cells	n/a	xxx	xxx
	Neutrophils	n/a	xxx	xxx
	NK-cells	n/a	xxx	xxx
	T-cells	n/a	xxx	xxx
	B-cells	n/a	xxx	xxx
Day 4 (Post Vaccination 2 vs. Pre-Vaccination 2)	Monocytes	n/a	xxx	xxx
	Dendritic cells	n/a	xxx	xxx
	Neutrophils	n/a	xxx	xxx
	NK-cells	n/a	xxx	xxx
	T-cells	n/a	xxx	xxx
	B-cells	n/a	xxx	xxx
Day 8 (Post Vaccination 2 vs. Pre-Vaccination 2)	Monocytes	n/a	xxx	xxx
	Dendritic cells	n/a	xxx	xxx
	Neutrophils	n/a	xxx	xxx
	NK-cells	n/a	xxx	xxx
	T-cells	n/a	xxx	xxx
	B-cells	n/a	xxx	xxx
N=Number of subjects in the Omics analysis population DE Gene = differentially expressed gene				

Table 127: Genes Differentially Expressed Between Treatment Groups by Immune Cell Type, and Post-Vaccination Day

Table 127: Genes Differentially Expressed Between Treatment Groups by Immune Cell Type, and Post-Vaccination Day

		Study Arm 2 A/H7N9 + AS03, D1, 29 (N=X) vs. Study Arm 3 A/H7N9 + PBS, D1, 29 (N=X)	Study Arm 2 A/H7N9 + AS03, D1, 29 (N=X) vs. Study Arm 1 A/H3N2v, D1 (N=X)	Study Arm 3 A/H7N9 + PBS, D1, 29 (N=X) vs. Study Arm 1 A/H3N2v, D1 (N=X)
Time Point	Cell Type	DE Genes [#]	DE Genes [#]	DE Genes [#]
Day 2 (Post Vaccination 1 vs. Pre-Vaccination 1)	Monocytes	xxx	xxx	xxx
	Dendritic cells	xxx	xxx	xxx

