	Neutrophils	xxx	xxx	xxx
	NK-cells	xxx	xxx	xxx
	T-cells	xxx	xxx	xxx
	B-cells	xxx	xxx	xxx
Day 4 (Post Vaccination 1 vs. Pre-Vaccination 1)	Monocytes	xxx	xxx	xxx
	Dendritic cells	xxx	xxx	xxx
	Neutrophils	xxx	xxx	xxx
	NK-cells	xxx	xxx	xxx
	T-cells	xxx	xxx	xxx
	B-cells	xxx	xxx	xxx
Day 29 (Post Vaccination 1 vs. Pre-Vaccination 1)	Monocytes	xxx	n/a	n/a
	Dendritic cells	xxx	n/a	n/a
	Neutrophils	xxx	n/a	n/a
	NK-cells	xxx	n/a	n/a
	T-cells	xxx	n/a	n/a
	B-cells	xxx	n/a	n/a
Day 2 (Post Vaccination 2 vs. Pre-Vaccination 2)	Monocytes	xxx	n/a	n/a
	Dendritic cells	xxx	n/a	n/a

		Study Arm 2 A/H7N9 + AS03, D1, 29 (N=X) vs. Study Arm 3 A/H7N9 + PBS, D1, 29 (N=X)	Study Arm 2 A/H7N9 + AS03, D1, 29 (N=X) vs. Study Arm 1 A/H3N2v, D1 (N=X)	Study Arm 3 A/H7N9 + PBS, D1, 29 (N=X) vs. Study Arm 1 A/H3N2v, D1 (N=X)
	Neutrophils	xxx	n/a	n/a
	NK-cells	xxx	n/a	n/a
	T-cells	xxx	n/a	n/a
	B-cells	xxx	n/a	n/a
Day 4 (Post Vaccination 2 vs. Pre-Vaccination 2)	Monocytes	xxx	n/a	n/a
	Dendritic cells	xxx	n/a	n/a
	Neutrophils	xxx	n/a	n/a
	NK-cells	xxx	n/a	n/a
	T-cells	xxx	n/a	n/a
	B-cells	xxx	n/a	n/a
Day 8 (Post Vaccination 2 vs. Pre-Vaccination 2)	Monocytes	xxx	n/a	n/a
	Dendritic cells	xxx	n/a	n/a
	Neutrophils	xxx	n/a	n/a
	NK-cells	xxx	n/a	n/a
	T-cells	xxx	n/a	n/a
	B-cells	xxx	n/a	n/a
N=Number of subjects in the Omics analysis population DE Gene = differentially expressed gene				

Table 128: Genes Differentially Expressed at Day 2 Compared to Pre-First Vaccination (RNA-Seq, Monocytes, Study Arm 1 A/H3N2v, D1)

Generate tables for each applicable post-vaccination day, treatment group, pairwise treatment group comparisons (Group 1 vs. 2, Group 1 vs. 3, Group 1 vs. 3, and Group 2 vs. 3), and cell type (monocytes, neutrophils, dendritic cells, NK cells B cell, and T cells). For Group 1 include tables for days 2, 4, and 8 post-first vaccination. For Groups 2 and 3 provide tables for post-vaccination days 2, 4, 29, 30, 32, and 36 post-first vaccination. For pairwise group comparisons that include Group 1, generate tables for days 2 and 4 post-first vaccination. Otherwise, prepare comparison results for days 2,4, 29, 30, 32, and 36 post-first vaccination.

Ensembl Gene ID	Ensembl Gene Name	Ensembl Gene Description	Gene Type	Log ₂ Fold Change (Day 2 vs. Pre-First Vaccination)	Average Log ₂ CPM*	Likelihood Ratio Test Statistic	P-Value	FDR Adjusted P-value

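### The likelihood ratio test for differentially expressed genes leaves 9 residual df; with the usual chi-square reference, the false share among called genes can exceed the 5% FDR the SAP claims to control

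*SAP*

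**What the plan says.** SAP 9.2.1 fits one negative binomial model per arm and post-vaccination day in edgeR, with a dummy variable for each subject and one for vaccination. For each gene "the statistical significance of the post- vs. pre-vaccination effect will be evaluated using a likelihood ratio testing the following hypothesis" of no change. The reference is one combined pre-vaccination sample per subject (SAP 9.1.4). For the second dose, SAP 9.2.2 states: "The model will be parameterized and evaluated as described in Section 9.2.1, except using Day 29 as the pre-vaccination reference". SAP 9.2.3 extends the model to pairs of arms through contrasts without naming the test. The gene listing, Table 128, is to be produced for these comparisons too and has a column headed "Likelihood Ratio Test Statistic". SAP 9.2 likewise says that "FDR-adjusted p-values, likelihood ratio statistic and average LCPMs will be provided for each post-vaccination day".

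A gene is called when its Benjamini-Hochberg adjusted p-value is below 0.05 and its fold change is at least 1.5. SAP 9.2 adds that, depending on the effects seen, "the pre-specified fold change cut off of 1.5-fold may be revised". On the number of genes tested, SAP 9.1.6 says: "The goal is to choose a cut off that retains between 10,000 and 14,000 genes for differential analysis". SAP 6.8 says that the FDR procedure "will be used to control the false positive rate among significantly differentially expressed genes, proteins, and enriched pathways".

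The reference distribution, the dispersion estimator and any small-sample correction are not stated.

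**The concern.** Benjamini-Hochberg keeps its promise only if very small p-values are calibrated. A likelihood ratio test read against chi-square treats the dispersion as known. When it is estimated from few residual df, even after moderation across genes, its uncertainty is ignored and the far tail is too heavy. Rates at p < 0.05 can look correct while rates at p < 0.001 do not.

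Primary endpoint 3 is the number of called genes, tabulated in Table 126 ("Genes Differentially Expressed Compared to Pre-Vaccination by Treatment Group, Cell Type, and Post-Vaccination Day"). The same gene lists go on to the clustering, pathway and network analyses in SAP 9.3. A reader will take each count as having at most 5% false calls, because SAP 6.8 says so.

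**Working it through.** **Degrees of freedom.** From SAP 4.1 and 9.2.1, with 10 subjects per arm:
- Within an arm: 2 × 10 = 20 observations, 10 subject terms + 1 vaccination term = 11 coefficients, 20 − 11 = 9. The rank of the design matrix confirms this. Each lost pair removes two observations and one coefficient, so one more df.
- Between two arms: 2 × 20 = 40 observations, 20 + 2 = 22 coefficients, 40 − 22 = 18.

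**Models behind primary endpoint 3.** 2 arms × 6 days × 6 cell types = 72.

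**Where the cut-off falls.** With 12,000 genes tested and k called by Benjamini-Hochberg, the p-value cut-off is 0.05 × k / 12,000. For k = 585 it is 0.0024; for k = 24 it is 0.0001. The far tail therefore decides the calls.

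**Upper bound, no moderation.** If a t statistic on 9 df is read as chi-square on 1 df, nominal p of 0.05 / 0.001 / 0.0001 is really 0.082 / 0.0094 / 0.0037. The ratios are 1.6, 9.4 and 37. edgeR moderates dispersions across genes, so the actual excess is smaller.

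**Simulation in edgeR 4.0.16.** 10 pairs, 12,000 genes, TMM, estimated dispersions, 3 runs per setting. Assumed, because the documents give no values: the biological coefficient of variation (its square is the dispersion), the prior df for gene-to-gene dispersion, and the share of truly changed genes (|log2 fold change| 0.6-2). Where dispersion varied by gene, null p < 0.05 occurred in 4.6-5.3% of genes, p < 0.001 2.1-2.7 times too often and p < 0.0001 3.4-9.1 times too often. False share at FDR < 0.05, before / after the 1.5-fold filter:

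| Dispersion | Prior df | True genes | Likelihood ratio | Quasi-likelihood F |
|---|---|---|---|---|
| 0.04 | 10 | 2% | 10.4% / 4.1% | 4.4% / 2.1% |
| 0.04 | 4 | 2% | 13.1% / 10.9% | 4.3% / 4.0% |
| 0.16 | 10 | 2% | 11.2% / 11.2% | 2.5% / 2.5% |
| 0.16 | 10 | 10% | 7.2% / 7.2% | 3.8% / 3.8% |
| 0.16 | common to all genes | 2% | 4.1% / 4.1% | 3.0% / 3.0% |

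A further set of edgeR runs gave, after the filter, 1-3% at dispersion 0.04, 5-8% at 0.08 and 9-12% at 0.15, against 0.6-3.7% for the F-test.

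**Larger simulation in a separate Python implementation.** 40 runs × 12,000 genes per setting, 5% true genes (|log2 fold change| 0.6-1.5), prior df 5 or 10, summed or single baseline. Over 10 within-arm settings, null p < 0.05 occurred in 4.8-5.7% of genes, p < 0.001 2.2-3.5 times and p < 0.0001 5-10 times too often; for F the two ratios were 0.7-1.1 and 0.6-1.1. After the filter:

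| Setting | Likelihood ratio | F |
|---|---|---|
| Dispersion 0.04 | 0.9-3.8% | 0.7-1.8% |
| Dispersion 0.08 | 6.3-9.0% | 3.7-3.9% |
| Dispersion 0.15 | 9.4-12.8% | 3.1-5.0% |
| Between arms, 18 df, dispersion 0.08, prior df 10 | 7.2% | 4.2% |
| Post-vaccination dispersion doubled | 15.0% | 7.0% |

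In genes (summed baseline, prior df 10), called and false:
- Dispersion 0.08: likelihood ratio 585, 37 false (6.3%); F 555, 21 false (3.8%).
- Dispersion 0.15: likelihood ratio 519, 57 false (11.0%); F 425, 22 false (5.2% as a ratio of these counts).

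**No true effect at all.** In Python, at dispersion 0.08 or 0.15, at least one gene was called in 80-98% of runs (mean 2.8-6.2 genes), against 3-8% of runs for F. In edgeR the result varied more. The three-run set gave no calls at dispersion 0.04 and two genes over three runs at 0.16. The further set gave at least one call in 50-100% of runs (mean 1.75-6 genes), with almost none for F.

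**The case against.** The strongest case against has four parts.

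- **Unknown inputs.** The SAP does not say chi-square, and the dispersions are unknown. With low dispersion the 1.5-fold filter can bring the false share under 5%, and with one common dispersion there was no inflation. This stands as a limit on size. It does not remove the problem: one low-dispersion edgeR setting still gave 10.9% after the filter, and the filter itself may be revised, in either direction.
- **Small excess.** At dispersion 0.08 and prior df 10, 37 of 585 calls are false. Five percent of 585 is 29, so the excess is about 8 genes. This stands for that setting; at 0.15 it is 57 against 26 (5% of 519).
- **A trade-off.** At 0.15 the F-test finds 425 − 22 = 403 true genes against 519 − 57 = 462, so it loses 59 true genes to remove 35 false ones. Protocol 11.2 calls the study hypothesis-generating, and preferring sensitivity is defensible. But then SAP 6.8 should not claim that the false positive rate is controlled.
- **Downstream safeguards.** Clusters and pathways have their own thresholds (SAP 9.3.2 and 9.3.3), and how far false calls carry into them was not measured. That is correct. The primary gene count has no such second screen.

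The chance of at least one call under no effect also depends on correlation between genes, which the simulations as described do not model. The mean number of false calls does not depend on it.

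**Conclusion.** The concern holds. The specified test has 9 residual df within an arm and 18 between arms. Read against chi-square with gene-specific dispersions, it produces too many very small p-values. After both calling criteria, the false share ranges from within the claimed 5% at most low-dispersion settings to about 13% at dispersion 0.15, or 15% if vaccination doubles the dispersion. The direction does not depend on the assumed values as long as dispersion differs between genes; the size does. The summed baseline in SAP 9.1.4 is a valid paired reference and is not the cause.

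No confirmatory decision rests on the count, so this does not block the study. It should be changed because it affects a primary endpoint and a claim the SAP makes about it. Confidence is medium, since the dispersions, the prior df and the chi-square reference are assumptions.

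**What to change.** In SAP 9.2.1, replace the likelihood ratio test with edgeR's quasi-likelihood F-test. SAP 9.2.2 follows by reference; state in 9.2.3 that its contrasts use the same test. Name the dispersion method: trended negative binomial dispersion plus moderated quasi-dispersion. In SAP 9.2 and Table 128, list the F statistic and its denominator df instead of the likelihood ratio statistic. Leave SAP 9.1.4 as it is.

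This changes SAP wording, one table column and a few lines of R, and needs no new data. The price is fewer calls, including true ones: in the simulation true genes found fell by 0.2-2% at dispersion 0.04, 2-11% at 0.08 and 13-32% at 0.15. The F-test is slightly conservative with the single Day 29 baseline and still somewhat liberal (7.0%) when subjects' responses differ strongly.

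If the team prefers to keep the likelihood ratio test for sensitivity, SAP 6.8 should describe the FDR as nominal and the F-test counts should be reported beside it.

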9.2.2. Identification of DE Genes Compared to Pre-Second Vaccination

For subjects receiving a second vaccination, for each post-second vaccination day (Day 30, 32, and 36) and study arm (Study Arms 2 and 3), a negative binomial model will be fit to pre- and post-second vaccination read counts across subjects. The model will be parameterized and evaluated as described in Section 9.2.1, except using Day 29 as the pre-vaccination reference.

9.3.1. Subject-level Response Heatmaps

Per-subject baseline \log_2 fold change patterns for DE genes will be visualized across Study Arms for each post-vaccination day and fold change set (post-first vaccination and post-second vaccination) using heatmaps (Figure 11, left panel). Genes identified as DE for any of the comparisons described in Section 9.2 will be included as part of this analysis. Heatmaps will include subject and gene dendrograms based on uncentered Pearson correlation distance and complete linkage hierarchical clustering.

9.3.2. Identification of Co-Expressed Gene Clusters

Unsupervised multiscale bootstrapping as implemented in the pvclust R package [12] will be carried out to identify robust clusters of genes with correlated \log_2 fold change responses for each fold change set (post-first vaccination and post-second vaccination). Bootstrap resampling will be based on uncentered Pearson correlation distances between \log_2 fold change responses in combination with complete linkage clustering. Genes identified as DE for any of the comparisons described in Section 9.2 will be included as part of this analysis. Clusters with a bootstrap probability > 0.95 and maximum distance between cluster members of 0.5 (equivalent to minimum uncentered Pearson correlation of 0.5 among all members) will be considered robust gene clusters. Resulting robust gene cluster dendrograms will be visualized (Figure 11, middle panel) and cluster information will be tabulated (Table 129). In addition, mean \log_2 fold change for robust gene clusters (mean across all member genes in a cluster) and associated 95% bootstrap CIs (1000 replicates each) will be visualized by study arm across the respective post-vaccination days (Figure 11, right panel).

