4. INVESTIGATIONAL PLAN

4.1. Overall Study Design and Plan

This is a single center, randomized, partially-blinded, Phase II, small, targeted, prospective study in approximately 30 healthy male and non-pregnant female subjects aged 18 to 49 years old, inclusive, designed to evaluate and compare the immunogenicity between an intramuscular monovalent inactivated influenza A/H7N9 virus vaccine manufactured by Sanofi Pasteur given with and without AS03 adjuvant manufactured by GlaxoSmithKline, and an intramuscular unadjuvanted monovalent inactivated influenza A/H3N2v virus vaccine manufactured by Sanofi Pasteur.

This study will use a standard and systems biology approach to assess the human early gene and protein signatures expressed at baseline (approximately Days -7 and 1), and at approximately Days 2, 4, and 8 (A/H3N2v-vaccinated subjects only) after the first study vaccination in each treatment arm as well as at approximately Days 29, 30, 32, and 36 in A/H7N9-vaccinated subjects only. Cellular immunogenicity (systems biology studies) data will be integrated with serologic immunogenicity (HAI and Neut antibody assays) and reactogenicity data to develop a systems model of the human immune response to unadjuvanted monovalent inactivated influenza A/H3N2v virus vaccine and monovalent inactivated influenza A/H7N9 virus vaccine given with and without AS03 adjuvant.

This study will use venous blood samples and subject data collected from a total of thirty vaccinated subjects randomly divided into three equal treatment arms (Table 1). The first treatment arm (n=10) will be vaccinated with one dose of 15 µg of A/H3N2v HA. The second treatment arm (n=10) will be vaccinated with two doses of 3.75 µg of A/H7N9 HA given with AS03 approximately 28 days apart. The third treatment arm (n=10) will be vaccinated with two doses of 3.75 µg of A/H7N9 HA given without AS03 adjuvant approximately 28 days apart. All study vaccinations will be administered intramuscularly.

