8.2. Plasma Cytokines/Chemokine Analysis

Pre-first vaccination cytokine/chemokine concentration will be determined using the mean concentrations among pre-vaccination measurements at Day -7 to -1 and Day 1. Cytokine/chemokine concentrations as well as their baseline fold changes will be summarized using minimum, Q1, median, Q3, maximum, and 95% CI of the median (starting with Table 26 and ending with Table 121). The 95% CI of the median concentration and median fold change from baseline will be determined by using the bootstrap method using 1,000 bootstrap replicates and will be visualized using time trend plots (Figure 4) and radar plots (Figure 5). To identify cytokines/chemokines that show a differential response from baseline, a two-sided Wilcoxon signed-rank test will be carried out for each study arm and post-vaccination time point (Table 122, Table 123). Significant differences in fold changes between study arms for shared post-vaccination time points will be evaluated using a Wilcoxon rank-sum test (Table 124, Table 125). Data listings of cytokine/chemokine assay results will be provided as shown in Listing 9 sorted by study group, subject ID, and visit.

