9.3.3. Pathway Enrichment Analysis

Pathway enrichment analysis will be carried out separately for each DE gene set identified (post vs. pre-vaccination as well as between study arm comparisons) using published pathway information obtained from KEGG [13] (KEGG Pathways), MSigDB [14] (MSigDB Reactome Pathways, MSigDB GO Biological Process, and MSigDB Immunologic Signatures), and Blood Transcription Modules [15]. Pathway enrichment analysis will be conducted using the goseq algorithm [16] to adjust for RNA-Seq-specific gene length bias¹. Pathways with a FDR-adjusted p-value < 0.05 will be considered significantly enriched. Due to the relatively increased number of pathways in the MSigDB Immunologic Signatures set, a more stringent FDR-adjusted

¹ For RNA-Seq, longer genes tend to obtain higher read counts compared to shorter genes as they occupy a higher proportion of the transcriptome/genome space. As such gene expression based on read counts is not only proportional to the actual expression but a combination of read length and actual expression. This results in greater statistical power for detecting differential genes if they are long and highly expressed. The effect needs to be addressed in gene set enrichment analysis as comparisons are made between sets of genes. Otherwise gene sets that on average contain larger genes will more likely be identified as significantly enriched compared to gene sets with on average smaller genes.

p-value < 0.01 will be used. Pathway enrichment results including gene set annotation, gene set size, number of DE genes in a gene set by up and down-regulation, Jaccard similarity index, p-value, and FDR-adjusted p-value will be listed (Table 130). For enriched KEGG pathways, log₂ fold change from baseline will be overlaid on top of pathway maps and significantly up/and down-regulated genes (DE genes) will be highlighted to facilitate visual interpretation (Figure 12, left panel). Overlap between sets of identified enriched pathways will be summarized using UpSet plots (similar to Figure 10). Gene set enrichment trends across study arms and post-vaccination days will be visualized using heatmaps color-coded by enrichment score ($-1 \times \log_{10}(\text{enrichment p-value})$) (Figure 12, middle panel) as well as time trend plots of median pathway responses (based on median average log₂ fold changes of all pathway members) and associated 95% bootstrap confidence intervals (CIs) (similar to Figure 11, right panel).

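### SAP 9.3.2 and 9.3.3 leave the bootstrap type and resampling unit open; with about 10 subjects per arm, the usual 95% interval for a cluster mean covers about 90%

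*SAP*

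**What the plan says.** SAP 9.3.2 summarises each cluster by its average log2 fold change and adds a bootstrap interval, shown by arm and day: "mean across all member genes in a cluster) and associated 95% bootstrap CIs (1000 replicates each) will be visualized by study arm". SAP 9.3.3 plans the same kind of trend plot for pathways, with a median over "fold changes of all pathway members) and associated 95% bootstrap confidence intervals". The Figure 11 shell repeats the bootstrap label and adds nothing on method. Neither section states the interval type (percentile, basic, BCa or studentised) or the unit that is resampled.

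A cluster counts as robust partly through a maximum-distance rule, "equivalent to minimum uncentered Pearson correlation of 0.5 among all members".

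SAP 4.1 gives the sample: "a total of thirty vaccinated subjects randomly divided into three equal treatment arms", so about 10 per arm.

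For comparison, SAP 8.1 uses t-distribution intervals for geometric mean titers in the same arms. SAP 8.2 uses a bootstrap for cytokine medians ("determined by using the bootstrap method using 1,000 bootstrap replicates"), as Protocol 11.5.3 prescribes.

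**The concern.** Two choices that set the width of these bands are left to the programmer.

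- **Interval type.** At n=10 the standard bootstrap intervals for a mean are too short. The bootstrap standard error lacks the n/(n-1) correction, and the percentile method does not allow for the standard deviation being estimated from 10 values.
- **Resampling unit.** Both statistics are described as summaries over genes, so a programmer could resample genes. That measures how much member genes differ from one another. It does not measure how well 10 people determine the arm's response.

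Two programmers following the same text could therefore draw bands of very different width under the same 95% label. These plots show the AS03 and no-AS03 trajectories by arm and day, and understanding how AS03 changes the response is the study's main scientific aim.

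**Working it through.** The SAP gives no calculation behind the 95% label, so there is no figure to reproduce. The check is the coverage that each reading would deliver.

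**Inputs.** From the SAP: nominal 95%, 1,000 replicates for clusters, about 10 subjects per arm; n=8 is added to allow for lost samples. Assumed, because the documents do not give them: subject SD 0.7 log2, mean log2 fold change 0.6-2, 3-50 genes per cluster, SD between gene means 0.1-0.3, between-subject correlation of genes 0-0.8.

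**1. Subjects resampled, cluster mean.** Averaging over genes and then subjects equals averaging each subject's cluster mean, so this is a bootstrap of a mean of n values. The percentile half-width is approximately 1.96 × sqrt((n-1)/n) × s/sqrt(n), and for normal data coverage is P(|t with n-1 df| < 1.96 × sqrt((n-1)/n)).

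- n=10: 1.96 × sqrt(9/10) = 1.86; coverage 90.4%.
- n=8: 1.96 × sqrt(7/8) = 1.83; coverage 89.1%.
- The t multiplier with 9 df is 2.262, and 2.262/1.86 = 1.22, so a t interval is about 22% wider at n=10.

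Simulated coverage (2,500 data sets per setting, 1,000 replicates each):

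| Data, n | Percentile | Basic | BCa | Bootstrap-t |
|---|---|---|---|---|
| Normal, 10 | 90.1% | 90.4% | 89.8% | 94.8% |
| t with 5 df, 10 | 89.8% | 91.4% | 88.6% | 94.0% |
| Exponential, 10 | 86.3% | 84.1% | 88.4% | 94.1% |
| Normal, 8 | 88.7% | 88.4% | 88.3% | 94.9% |

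The pathway median was not simulated separately.

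**2. Genes resampled, cluster mean, n=10** (assumed grid):

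- Between-subject correlation 0.5-0.8: from 14% (50 genes, correlation 0.8, gene-mean SD 0.1) to 80% (5 genes, correlation 0.5, gene-mean SD 0.3).
- Correlation 0.2, with 5-50 genes and mean log2 fold change 2: 44-87%.
- Correlation 0: 77-99.8%.

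**3. Does the 0.5 rule settle the correlation?** No. For two genes with common mean m, SD s and ordinary (centered) correlation r, the expected uncentered correlation is about (m² + r s²)/(m² + s²). With m=2, s=0.7 and r=0 this is 4/4.49 = 0.89. Genes that share a large mean response can therefore pass the rule with no between-subject correlation at all.

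**4. Cytokine medians (SAP 8.2), subjects resampled, percentile.** 93.4-93.8% at n=10 and 91.8-91.9% at n=8.

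**The case against.** The strongest reply has four parts.

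- **The text does not require a poor interval.** A reader might infer that these intervals cover 90% at best. The documents do not support that: a bootstrap-t over subjects satisfies the wording and covers about 94-95%. The defect is an open specification whose usual execution falls short. This stands.
- **Gene resampling is conjecture.** SAP 9.1.5 computes fold changes for each subject and SAP 9.3.1 displays them by subject, which points towards subjects. A reader might also infer that the 0.5 rule guarantees strong between-subject correlation, and hence coverage of 10-50%. Step 3 shows that it does not. This stands, but the SAP does not exclude gene resampling.
- **No inference uses the bands.** Arms are compared by edgeR contrasts with false-discovery-rate control (SAP 9.2.3) and by Wilcoxon tests for cytokines (SAP 8.2). Protocol 11.2 calls the study exploratory and hypothesis-generating. This stands and limits the importance.
- **Short bands need not create false differences between arms.** Judging two arms by non-overlap of separate intervals is conservative. With no true difference, n=10 per arm and percentile intervals over subjects, the mean intervals failed to overlap in 1.7% of 3,000 simulated runs, below 5%. This stands for subject resampling. It was not checked for gene resampling or for comparisons between days.

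**Conclusion.** The point holds as a specification gap with a measurable consequence. With subjects resampled, percentile, basic and BCa intervals for a cluster mean miss about 10% of the time at n=10 under normality, twice the labelled 5%, and miss more often with strongly skewed data. With genes resampled, coverage could be roughly 15-80% if between-subject correlation is 0.5-0.8. That range rests entirely on assumed cluster sizes, spreads and correlations, and coverage can be nominal or higher when the correlation is zero. The pathway bands share the same open choices; their coverage was not computed. Any further loss from choosing the plotted genes because they were differentially expressed was not computed either.

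The harm is mislabelled precision in exploratory trend plots. It does not reach the formal comparisons. A reader might extend the point to the cytokine medians, but the percentile shortfall there is only 1-3 points and the protocol itself prescribes the bootstrap, so the documents give no reason to replace it.

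**What to change.** In SAP 9.3.2 and 9.3.3, state that the subject is the unit of analysis. For each arm and day, compute each subject's cluster mean (or pathway median) log2 fold change, then show the arm mean with a t-based 95% interval, as SAP 8.1 does for geometric mean titers. If a bootstrap is preferred, resample subjects and use a studentised interval. For pathways, the text should say explicitly that the plotted value is the arm mean of subject-level medians, because this may differ from a median of gene averages.

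The cost is one sentence per section, a matching note on the Figure 11 shell, and a few lines of code using the per-subject fold changes that SAP 9.1.5 already produces. Cluster bands become about 22% wider at n=10 than percentile bands over subjects. SAP 8.2 and Protocol 11.5.3 need no change.
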